9.3.1 Protocol Definition of a Pulmonary Exacerbation

The presence of a protocol-defined pulmonary exacerbation is defined by the following, the criteria of Fuch et al. ⁹⁴: "Exacerbation of respiratory symptoms": a patient treated with parenteral antibiotics for any 4 of the following 12 signs or symptoms:

Change in sputum	New or increased hemoptysis	Increased cough
Increased dyspnea	Malaise, fatigue or lethargy	Temperature above 38°C
Anorexia or weight loss	Sinus pain or tenderness	Change in sinus discharge

Change in physical
examination of the chest

Decrease in pulmonary function by
10 percent or more from a previously
recorded value

Radiographic changes indicative of
pulmonary infection

This definition is not a guide to determine the need for a given type of treatment (for example: Oral versus IV antibiotics, corticosteroids or no). Each Investigator will determine to the best of its clinical judgement and for the benefit to the patient, the best treatment for the exacerbation episode. However, if indeed an IV antibiotic course is selected based on the severity of the PEx and other factors and the patient can attend the study site prior to starting the IV antibiotics, this will trigger the performance of PEx-specific assessments prior to initiating the IV antibiotic course and at the end of the course. This is outlined below:

9.3.2 Specific additional testing for patients undergoing a pulmonary exacerbation treated with an IV antibiotic treatment cycle.

Prior to starting and after completing the IV antibiotic treatment:

1. Blood sampling for selective biomarkers such as:
 - a. Plasma lipidomics: AA, DHA, calculated AA/DHA ratio and EPA;
 - b. Markers of inflammation in:
 - Whole blood: total white cell count and absolute neutrophil count;
 - Serum: high sensitivity C-Reactive Protein (hsCRP) and serum amyloid A (SAA);
 - Plasma: interleukins IL-1ra, IL-6, IL-8, IL-10, Granulocyte-Colony Stimulating Factor (G-CSF), calprotectin, ceruloplasmin, haptoglobin, and neutrophil elastase antiprotease complexes (NEAPC).
2. Clinical parameters such as FEV₁ percent predicted, weight, with BMI calculated.

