3.3 Analysis Population

The Intent-to-treat (ITT) Population will include all patients randomized to a treatment group who complete the baseline evaluations, regardless of having received any study treatment or not. The ITT population will be used for the primary analyses of all study endpoints, taking into consideration the specific populations described below. The patients will be kept in their randomized treatment arm for the analyses.

The Per Protocol (PP) Population will include all patients randomized to a treatment group to whom at least 5 cycles of study treatment are administered in accordance with the protocol, defined as at least 80% compliance. The PP population will serve as the basis for secondary analyses of

all study endpoints, taking into consideration the specific populations described below. The patients will be kept in the treatment arm that they actually received for the analyses.

The FEV₁ Population is a subset of the PP population and will include all patients who have validated FEV₁ values (values judged to be obtained from adequate expiratory curves by central review) for at least 4 time points of the study comprising at the minimum the baseline and Day 161 assessments. This population will be used for the secondary analyses of all FEV₁-related endpoints. The patients will be kept in the treatment arm that they actually received for the analyses.

The Protocol-Defined PEx Subset Population will include all patients who experience a protocol - defined PEx episode (\geq 4/12 Fuch symptoms and use of IV antibiotic) during the study after completing at least one cycle of study drug treatment. The patients will be kept in the treatment arm that they actually received for the analyses.

The Overall PEx Subset Population will include all patients who experience an oral or IV antibiotic treated PEx episode during the study after completing at least one cycle of study drug treatment. The patients will be kept in the treatment arm that they actually received for the analyses.

The Safety Population will include all patients randomized to a treatment group who received at least one dose of study drug treatment. This population will serve as the basis for analyses of all safety endpoints. The patients will be kept in the treatment arm that they actually received for the analyses.

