3.15 Analysis of the Secondary Endpoints

For all secondary efficacy endpoints, all the analysis will be based on data obtained at Week 24 or cumulated up to Week 24

Pre-defined Clinical Parameters:

- Count data variables: the number of antibiotic treatments, the number of days of antibiotic treatment (other than chronic inhaled antibiotics already started prior to trial or oral chronic azithromycin, in summary, any antibiotic change required to address worsening of CF symptoms) and the number of PEx and protocol-defined PEx will be tabulated by treatment group and compared using an appropriate count data model, e.g., Mixed ANOVA model (if assumptions of normality and homogeneity of variance appear acceptable), Poisson regression, negative binomial regression, zero-inflated regression, etc., depending on their distribution. The analysis of the number of protocol-defined PEx will also consider the type of antibiotic

prescribed (I.V. vs. oral) and the time spent on study as well as other covariates described below for the time to event data.

- Time to event data variables: the time to first antibiotic use, the time to first PEx and protocol-defined PEx, the time interval between IV antibiotic-treated PEx episodes will be tabulated by treatment group and compared using a Cox proportional hazards model. The model will include treatment group as main effect with covariates for FEV₁ percent predicted category (<70% versus ≥70% predicted), PEx number category in prior year (≤3 versus > 3 PEx episodes), and co-administration or not of Kalydeco® (ivacaftor), Orkambi® (ivacaftor/lumacaftor), Symdeko® (ivacaftor/tezacaftor) or another commercially available CFTR modulator product (all as per entry stratification). A patient without exacerbation before withdrawal or completion of the study is considered censored at the time of withdrawal or completion of the study. If the proportional hazards assumption is violated, a stratified analysis will be conducted using stratified Cox regression. Additionally, Kaplan-Meier methods will be used to produce graphical presentations of the survival (exacerbation-free survival) by treatment group and to estimate cumulative exacerbation-free survival rates by treatment group.
- Relative change (in %) in FEV₁ percent predicted from Baseline to Week 24: analysis of this variable will be similar to that of the primary analysis of the primary efficacy endpoint, i.e. repeated measures mixed model.

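### SAP 3.15 adjusts the protocol-defined PEx count for antibiotic route, although every such event is IV-treated by definition and route is chosen after randomisation

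*SAP*

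**What the plan says.** SAP 3.15, under count data variables, first lists candidate models: a Mixed ANOVA model if its assumptions look acceptable, or "Poisson regression, negative binomial regression, zero-inflated regression, etc., depending on their distribution". It then adds a rule for one outcome: "The analysis of the number of protocol-defined PEx will also consider the type of antibiotic", continuing "prescribed (I.V. vs. oral) and the time spent on study as well as other covariates described below for the time to event data".

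Protocol 9.3.1 defines the event being counted as "a patient treated with parenteral antibiotics for any 4 of the following 12 signs or symptoms". SAP 3.3 agrees: its Protocol-Defined PEx subset requires at least 4 of 12 "Fuch symptoms and use of IV antibiotic". A separate Overall PEx subset covers "all patients who experience an oral or IV antibiotic treated PEx episode during the study".

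On the analysis set, SAP 3.3 says "The ITT population will be used for the primary analyses of all study endpoints", so patients who never have a PEx are in the model.

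Protocol 12.4.2 specifies the same count analysis with time on study and the covariates of the time-to-event model. It does not mention route. SAP section 5, which lists methodological changes from the protocol, records the new Overall PEx outcome but not the addition of route.

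**The concern.** The SAP's wording puts route in a list with time on study and then refers to further covariates as the other ones, so route is itself a covariate. A covariate should be defined for every patient in the analysis set, able to vary, and not itself a consequence of treatment. Route fails all three here. It takes one value among counted events, it is undefined for patients who receive no antibiotic, and the investigator chooses it at each episode. Protocol 7.3 itself names the antibiotic route as something that knowledge of treatment could bias.

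The incidence of protocol-defined PEx is one of the trial's clinical secondary endpoints. If the sentence is followed literally, the treatment comparison for it is either restricted to a subset selected after randomisation or adjusted for something close to the outcome. If it is not followed, the programmer has to make an unplanned choice.

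**Working it through.** The documents give no figure for this model, so there is none to reproduce. The check compares the definitions with the covariate and then tries the plausible codings.

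**1. What route can be, by type of patient** (Protocol 9.3.1; SAP 3.3)

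| Patient's antibiotic use for PEx | Protocol-defined PEx count | Route |
|---|---|---|
| IV, at least 4 of 12 signs | 1 or more | IV |
| IV only, fewer than 4 signs | 0 | IV |
| Oral only | 0 | oral |
| None | 0 | undefined |

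A positive count implies IV, and oral or none implies a count of 0. The SAP gives no rule for a patient with both an oral and an IV course.

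**2. Codings tried on simulated data.** There was one data set at each of two risks, p = 0.30 and p = 0.15. Assumptions that are not in the documents: 68 patients per arm, equal follow-up, no treatment effect, Poisson counts with mean −ln(1 − p) (0.357 and 0.163), every IV-treated PEx counted as protocol-defined, and 35% of patients with some oral course. The models contained treatment, three binary stratification factors and route.

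- *Route read from the counted events.* Only 46 (p = 0.30) or 19 (p = 0.15) of 136 patients have a value, and all are IV. The design matrix has rank 5 for 6 columns: route duplicates the intercept. All patients with a count of 0 are lost.
- *IV versus oral or none, all patients.* Complete separation. At p = 0.30 the Poisson route coefficient is 11.8, 26.8 and 37.3 after 10, 25 and 50 iterations. Its standard error goes from about 22 to about 39,200 to about 5.2 million.
- *IV versus oral among patients with any antibiotic.* 76 patients (p = 0.30) or 55 (p = 0.15) remain. The coefficient again diverges (about 37, standard error above 8 million), because oral-only patients have a count of 0 by definition.
- *Route omitted.* The Poisson fit converges, with a standard error for the log rate ratio of 0.28 (p = 0.30) and 0.42 (p = 0.15).

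The exact numbers depend on the simulation, but the aliasing and separation follow from the table in step 1.

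**3. The Mixed ANOVA option.** A normal-theory model with IV versus oral or none would return finite estimates. Route then nearly restates whether the count is above 0, so adjusting for it removes much of any effect that treatment has on having an exacerbation. This step is reasoning and was not simulated.

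**4. How many patients cannot have a countable event.** Inputs: 136 randomised (SAP 2.6). Protocol section 6 gives about a 30% chance of an IV-treated PEx in 24 weeks for patients with an IV-treated PEx in the prior year, and odds about half that without one.

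- All patients at 30%: 136 × (1 − 0.30) = 95.2, about 95.
- Odds halved: 0.30/0.70 = 0.4286; half is 0.2143; 0.2143/1.2143 = 0.176; 136 × (1 − 0.176) = about 112.
- Risk halved to 15%: 136 × 0.85 = 115.6, about 116.

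These counts are of patients without an IV-treated PEx, who therefore have a protocol-defined count of 0. Some of them would still have an oral route.

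**The case against.** The strongest reply is that the sentence only says route will be considered, gives no coding, and sits under an open list of models, so it may mean a descriptive split. The reference to other covariates tells against this, and a split of protocol-defined events by route would have an empty oral column anyway.

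Four stronger readings are tempting, and the documents do not support them.

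- *That the analysis cannot be fitted at all.* This is not true of every listed model. Mixed ANOVA returns numbers, and in the count regressions an aliased or divergent route coefficient does not by itself stop a treatment estimate from being computed. The trouble is what that estimate means.
- *That every patient without an event lacks a route.* Patients treated orally, or with IV antibiotics for fewer than four signs, have a count of 0 and a route. Only patients without any antibiotic have none.
- *That 95 of 136 patients would have a missing covariate.* That figure counts patients without an IV-treated PEx, and it applies the prior-year-IV risk to everyone. Protocol 8.1 also admits patients whose prior PEx was treated orally, although Protocol 7.2.1 and SAP 2.4 and 2.7.1 still require IV.
- *That oral-treated events would slip into the endpoint.* Nothing in the text says so. SAP 3.15 already counts overall PEx as a separate outcome, so anyone wanting oral events has a planned place for them.

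It also stands that this is one of many secondary endpoints, tested without multiplicity control for signal detection (SAP 3.2), and that study success rests on FEV₁ alone (SAP 3.14).

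**Conclusion.** The point holds. Route does not belong in the protocol-defined PEx model: it is constant among counted events, undefined for some patients, and set after randomisation. Depending on the coding, the term is aliased and loses the patients without a value, is completely separated in the count regressions, or nearly restates the outcome in the Mixed ANOVA option. This rests on the definitions in Protocol 9.3.1 and SAP 3.3 and needs no assumed event rate.

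The illustrative size is about 95 of 136 patients without an IV-treated PEx if all carry the 30% risk, and about 112 to 116 if none had an IV-treated PEx in the prior year. The enrolled mix is not given, so the expected number lies between these limits. The number with no protocol-defined PEx would be at least as large, because four signs are also required.

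The error should be corrected, but it affects one secondary analysis and has no bearing on the primary FEV₁ conclusion.

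**What to change.** In SAP 3.15, remove the mention of antibiotic type from the sentence on the number of protocol-defined PEx. Keep time on study, as an offset, and the stratification covariates already listed for the time-to-event model. As in Protocol 12.4.2, the model then has no route term.

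Protocol 5.4.5.3 does intend oral and IV treatment of PEx to be distinguished. If that is wanted, report the planned overall PEx count separately for IV-treated and oral-treated episodes, by arm, as descriptive summaries. Route should not enter as a covariate, and no further tests are needed.

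The cost is one edited SAP sentence and, if the split is wanted, one summary table. It needs no new data and no change to trial conduct.

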10.10 Matouk Disease Score

The Matouk disease score will be determined at time points listed in the Schedule of Events, Page 10, specifically on Days 1, 77, 161, 189, (Visits #2, 5, 7 and 8, respectively), at selected sites who will volunteer to participate in this exploratory investigation. The objective of this investigation is to further validate the Score in the framework of a well controlled therapeutic study. An example of the subsection questionnaires is presented in the Study Reference Manual. Given the lack of recognized biomarkers for CF inflammation clinical studies, and the long time required for FEV₁ to show changes, we believe that exploring additional alternatives will be welcomed by the CF community.

The Matouk Disease Score was previously published^{97, 98}, and reviewed by Hafen⁹⁹ and was used recently in two studies; 1- A non-interventional study on pulmonary exacerbations by [name] and 2- A Phase Ib study of fenretinide^{3, 100}. Hafen recommends Matouk scoring as a potential tool to assess the clinical response to various treatment regimens on a short-term basis. The validation showed its value in prognostic evaluation of patients in end-stage disease, providing better discrimination for survival in the last 2 years of life than FEV₁ % predicted alone⁹⁸.

The Matouk Disease Score is a sum comprised of four subsections: clinical, pulmonary function tests (PFT), chest radiographic score (CXR) and complications score. The 3 key subsections with high impact on the total score internal consistency are the Clinical, the PFT and the Complication subsections. The CXR score is not essential for the Matouk score to perform well. If a new CXR is available, then its grading is used. Otherwise, the most recent CXR can be used instead. In the absence of a CXR, the radiographic score is omitted, and the total score internal consistency, as depicted by the Cronbach's coefficient alpha, is preserved. Consequently, the CXR score is optional.

The clinical subsection involves the evaluation of the patient's symptoms by the physician. The symptoms evaluated are weight, weight change, dyspnea, cough frequency, sputum colour, thickness and volume, physical examination (air entry, crackles, hyperinflation), respiratory rate/cardiac frequency, sputum culture, appetite and general condition.

The PFT subscore is based on the results of pulmonary function test.

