3.14 Analysis of the Primary Efficacy Endpoints

The study will be considered successful if a statistically significant advantage for fenretinide over placebo is obtained for the absolute change in FEV₁ percent predicted from baseline to Week 24, as assessed in the ITT population. Confirmatory analyses will be conducted in the PP Population, Protocol-defined PEx Population and Overall PEx Population.

Values for percent predicted FEV₁ as well as their change relative to baseline will be tabulated by time point and descriptive statistics will be used. In the analysis of the primary efficacy endpoint, the absolute change from Baseline in FEV₁ percent predicted, including all measurements up to Week 28 (both during and after treatment measurements, including after treatment discontinuation) will be analyzed based on a mixed model for repeated measures, with the following specifications:

- The dependent variables will be all the absolute changes in FEV₁ percent predicted from Baseline to each time point, including Week 28;
- The fixed effects will be the treatment group, the visit and the treatment-by-visit interaction;
- The random effect will be the patient;
- An unstructured variance-covariance structure will be adopted as the default structure; alternate variance-covariance structures may be adopted as appropriate.
- The model will be adjusted for the following *à priori* stratification categories:
 - FEV₁ percent predicted determined at Baseline (<70% versus ≥70% predicted),
 - PEx frequency in the prior year (≤3 versus > 3 PEx episodes),
 - Co-administration or not of Kalydeco® (ivacaftor), Orkambi® (ivacaftor/lumacaftor), Symdeko® (ivacaftor/tezacaftor) or another commercially available CFTR modulator product (yes versus no);

- The difference between treatment means at each time point and its 95% confidence interval will be estimated.
- Stratum-specific estimates based on Least Square Means will be generated

The primary result obtained from the model will be the treatment effect at Week 24. The estimated mean treatment effect, a 95% confidence interval, and a 2-sided p-value will be generated.

The analysis will be repeated with the addition of the following covariates in the model:

- Baseline use of Trikafta (yes versus no);
- Effect of the pandemic confinement (pre versus post pandemic onset) (described in Section 3.14.1)

Alternative methods will be used if necessary due to data not meeting the standard requirements for the proposed analysis.

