- Body weight and BMI changes from Baseline/Screening will be summarized using descriptive statistics by treatment group and compared between treatments using a linear mixed model similar to what is described under [Section 3.14](#), with the addition of the baseline parameter (Weight or BMI at baseline) as covariate in the model.

Quality of Life Endpoints:

- Quality-of-life data will be derived from the questionnaires according to the corresponding scoring manuals and will be summarized by treatment group. Patients' health state will be derived from the CFQ-R questionnaire, including the extracted CFQ-R respiratory domain, a separate endpoint. Additional exploratory health condition will be evaluated by the Matouk Disease Score. Data will be summarized by treatment group using descriptive statistics.

Analysis of the absolute change from baseline for the CFQ-R (overall and respiratory domain) as well as the Matouk Disease Score will be performed similarly to that of the primary efficacy endpoint with the addition of the CFQ-R score at baseline as a covariate for the analysis of the CFQ-R variables.

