3.17 Analysis of the Pharmacokinetic/Pharmacodynamics Endpoints

Pharmacodynamic Endpoints:

Values for AA, DHA and AA/DHA ratio as well as their change relative to baseline will be tabulated by time point and descriptive statistics will be used. The rate (frequency) of normalization (normalization meaning a parameter value reaching the mean parameter value observed in healthy controls ± 1 Standard Deviation) for AA, DHA, and the AA/DHA ratio will be calculated for the end-of-treatment cycle values, and the treatments will be compared using two-sided multivariate logistic regression with the respective baseline value as a covariate. Alternative methods will be used if necessary due to the data distribution. Healthy controls will consist of a group of approximately 20 healthy, non-CF adult subjects of both genders, not specifically matched to the APPLAUD CF patients.

Values for pharmacodynamic parameters (AA, DHA and AA/DHA ratio), EPA, inflammation markers, metabolipidomic markers, systemic bone formation/resorption markers, markers of oxidative stress, ceramides), as measured in plasma (or serum, or blood, as required), as well as their change relative to baseline, will be tabulated by time point and descriptive statistics will be used. An analysis of variance will be used to compare treatments assuming datasets meet standard pre-requisites for such analysis (normal or log-normal distribution and homogeneity of variance). Alternative methods will be used if necessary.

Pharmacokinetic Endpoints:

Blood samples for fenretinide C_{\min} analysis will be obtained from all patients randomized to fenretinide. Patients randomized to placebo will provide samples (to maintain the study blind) but will not contribute to the C_{\min} data.

Plasma fenretinide C_{\min} concentrations will be presented in a tabular summary, by sampling day and compared between groups of CF patients receiving fenretinide grouped according to the a-priori stratification factors, and assuming stratum size will allow such comparison.

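### As SAP 3.15 is worded, the Matouk change-score model leaves out the score's own Day 1 baseline, at some cost in precision

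*SAP*

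**What the plan says.** Under the quality-of-life heading of SAP 3.15, the analysis of change in CFQ-R "as well as the Matouk Disease Score will be performed similarly to that of the primary efficacy endpoint". The sentence ends by adding a baseline covariate, but ties it to one instrument: "with the addition of the CFQ-R score at baseline as a covariate for the analysis of the CFQ-R variables".

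The primary model in SAP 3.14 takes the changes from baseline as responses. It has treatment, visit and their interaction as fixed effects, and it adjusts for three dichotomies: FEV₁ below or at least 70% predicted, at most or more than three exacerbations in the prior year, and CFTR modulator use. SAP 3.16, on exploratory endpoints, does not mention Matouk.

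Two other analyses do carry the outcome's own baseline. Weight and BMI are modelled "with the addition of the baseline parameter (Weight or BMI at baseline) as covariate in the model" (SAP 3.15), and normalisation of AA, DHA and AA/DHA is compared "with the respective baseline value as a covariate" (SAP 3.17).

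The Matouk score is recorded "specifically on Days 1, 77, 161, 189" (Protocol 10.10), "at selected sites who will volunteer to participate in this exploratory investigation".

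**The concern.** A change score analysed without its baseline carries the measurement noise of the baseline reading as well as that of the follow-up reading, and it retains any chance difference between arms at Day 1. Randomisation is not stratified on the Matouk score (Protocol 7.3.3). The strata in the model are coarse, and they do not capture the symptoms, examination findings and complications that also make up the score (Protocol 10.10).

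The baseline value is already collected, so leaving it out saves nothing. What is at stake is the width of the confidence interval for an exploratory between-arm comparison.

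**Working it through.** **Inputs**
- Model terms: SAP 3.14, as listed above.
- Test level: two-sided 5% (SAP 3.1.1).
- Correlation rho between baseline and follow-up Matouk score within strata: not given; assumed 0.5 to 0.9.
- Number of patients N with Matouk data: not given; assumed 24 and 40, with the planned 136 as a reference point.
- The only sample-size figure in the plan is for FEV₁ (SAP 2.6). There is no Matouk figure to reproduce.

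**Step 1: does baseline Matouk enter by another route?** SAP 3.14 supplies only the three strata. SAP 3.15 adds a baseline for CFQ-R, and SAP 3.16 adds nothing. The repeated-measures structure does not bring it back, because the responses are changes and the Day 1 value is not itself a response. As worded, it is absent.

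**Step 2: variance at one follow-up visit.** Let both visits have variance s².
- Change score alone: 2(1 − rho)s².
- Baseline added as covariate: (1 − rho²)s².
- Ratio: (1 − rho)(1 + rho) / [2(1 − rho)] = (1 + rho)/2.

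For the same precision, the model as written needs 1/ratio − 1 more patients.

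**Step 3: charge for the extra coefficient.** The model as written has five coefficients at a single visit: intercept, treatment and three strata. Adding a sixth inflates the variance by about 1 + 1/(N − 7) and takes one residual degree of freedom. The ratio of confidence-interval widths, adjusted over unadjusted, is then

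√[(1 + rho)/2 × (1 + 1/(N − 7))] × t(0.975, N − 6) / t(0.975, N − 5).

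Example, rho 0.9 and N = 24: √(0.95 × 18/17) × 2.101/2.093 = 1.003 × 1.004 = 1.01.

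| Assumed rho | Variance ratio | Extra patients needed without baseline | CI width ratio, N = 24 | N = 40 | N = 136 |
|---|---|---|---|---|---|
| 0.5 | 0.75 | 33% | 0.89 | 0.88 | 0.87 |
| 0.7 | 0.85 | 18% | 0.95 | 0.94 | 0.93 |
| 0.8 | 0.90 | 11% | 0.98 | 0.96 | 0.95 |
| 0.9 | 0.95 | 5% | 1.01 | 0.99 | 0.98 |

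**Step 4: do the strata already do the job?** A simulation with N = 40 kept three binary strata in both models. In one setting the strata were unrelated to the score. In the other, each shifted it by half a within-stratum SD. The variance ratios were 0.75–0.76 at rho 0.5, 0.87–0.88 at rho 0.7 and 0.97–0.99 at rho 0.9. The strata do not remove the gain.

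**Step 5: unequal variances.** If the baseline SD is k times the follow-up SD, the ratio is (1 − rho²)/(1 + k² − 2k·rho). The denominator minus the numerator is (k − rho)², which is never negative. Before the cost in Step 3, adjustment therefore cannot lose. The size of the gain, however, is no longer (1 + rho)/2.

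**The case against.** The strongest reply is that little depends on this. Matouk change is an exploratory endpoint (Protocol 7.1.4, SAP 2.8.1.3), and the protocol plans only descriptive statistics for it (12.4.2). SAP 3.2 describes the non-primary analyses as mainly for signal detection. An unadjusted change score is a valid, if less efficient, analysis. All of that stands, and it makes this a minor point.

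It can also be said that own-baseline adjustment is not universal in the SAP: the analysis of variance for the other biomarkers in 3.17 names no covariate. That is so. But Matouk shares a sentence with CFQ-R and a model with weight and BMI, and no reason is given for treating it differently.

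The word *similarly* might be read loosely enough to include the baseline score. The closing clause points the other way, and if inclusion is intended the text still needs to say so. SAP 3.1.1 has table footnotes list the covariates. The table shells in Section 7 are not in the text reviewed, so the finding is limited to the wording of 3.15.

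A reader might go further than the documents allow in four ways:
- **That the subset is small, so baseline imbalance will be common.** No number of Matouk sites or patients is given. The limit of 24 patients applies to bone density (Protocol 10.9).
- **That power is lost by a known amount.** No Matouk power, SD or correlation is stated.
- **That adjustment is free at any size.** It costs one degree of freedom, which matters most in exactly the small subset that makes the concern look pressing.
- **That the result is biased.** Under randomisation it is not.

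**Conclusion.** The omission is real in the wording of SAP 3.15, and its consequence is modest. The Matouk comparison is unbiased but less precise than it could be, and the trial's success criterion is untouched.

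The variance reduction forgone is 25%, 15%, 10% and 5% at assumed correlations of 0.5, 0.7, 0.8 and 0.9, given equal variances at baseline and follow-up. After the small-sample cost, the gain is still visible at correlations up to 0.8 for each N examined, and it disappears at 0.9 with about 24 patients. Neither the correlation nor the subset size can be taken from the documents, so no single figure can be put on the loss.

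**What to change.** Reword the end of the CFQ-R and Matouk sentence in SAP 3.15 to: *with the addition of the respective baseline score (CFQ-R total, CFQ-R respiratory domain or Matouk score) as a covariate*. This also settles which CFQ-R baseline is meant. Protocol 12.4.2 names the respiratory domain score, while the SAP refers only to the CFQ-R score.

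Add that the baseline Matouk total is computed on the same components as the follow-up total, with or without the chest radiograph. Protocol 10.10 makes that component optional, and totals with and without it are not on one scale.

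The change should be made before treatment codes are released, so that the covariate is pre-specified. It costs one edited sentence and one degree of freedom, a negligible downside, and needs no new data.
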